9.10 Reportable Device Issues

Device deficiencies will be reported except in the following circumstances. These occurrences are expected and will not be reported on a Device Deficiency Form:

- CGM sensor, Pod or infusion set lasting fewer days than expected per manufacturer
- CGM tape, Pod or infusion set adherence issues
- Battery lifespan deficiency of the Controller due to inadequate charging or extensive wireless communication
- Intermittent device communication issues not requiring replacement
- Device issues, including alerts and alarms, clearly addressed in the user guide that do not require additional troubleshooting

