7.4.1 Randomization

Participants who meet all eligibility criteria, have completed all screening assessments, and have met the CGM device usage and data criteria will be randomized 2:1 using a computer-generated randomization scheme stratified by site, A1C (7% to <8% vs. ≥8% to 11%), and Omnipod use (user vs. non-user). A permuted-block randomization scheme will be implemented to balance group assignments. Randomization will be assigned via study database access during Visit 3 to the two study groups (Intervention Group: Omnipod 5 System with Dexcom G6 CGM or Control Group: Participant's current pump with Dexcom G6 CGM).

During the 13-week study period, all participants will be asked to do the following:

- Follow insulin therapy per recommendations from the clinical study staff
- Follow their pre-exercise management such as insulin reduction for meal boluses, consumption of snacks, or adjusting their insulin delivery settings
- Treat themselves per their usual routine if they become hypoglycemic or hyperglycemic or have symptoms of either at any time during the study
- Consume meals and snacks of their own choosing. Participants will be encouraged to estimate the grams of carbohydrates for each meal or snack per their usual routine. The estimate should be entered into the meal bolus calculator.
- Give meal boluses per their usual dosing routine
- Change their CGM per manufacturer's instructions or sooner if necessary
- Change the Pod at least once every 72 hours (Intervention group only)
- Change pump infusion site as recommended by manufacturer

In the event of unexplained hyperglycemia, where the CGM is >300mg/dL for 1 hour or >250 mg/dL for 2 hours, blood glucose (measured with BG meter) and ketones should be checked. If BG is ≥300 mg/dL and ketones are >1.0 mmol/L, an occlusion or dislodged cannula should be suspected. The Pod or infusion set should be removed, and the participant will be instructed to replace the Pod or infusion set at a different location on the body. Participants should contact the clinical site for further instructions to determine whether an additional injection of insulin is required. This prolonged hyperglycemic event, defined as meter BG ≥300 mg/dL and ketones >1.0 mmol/L, will be recorded as an adverse event.

7.5 Visits 4 and 5

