7.9 Early Withdrawal

Any participant may withdraw from the study at any time for any reason. Upon withdrawal, assessments will be performed following Table 1: Schedule of Assessments and Table 2: Patient Reported Outcomes (Questionnaires). The investigator may also terminate a participant's participation in the study if it is in the best interest of the participant or if the Sponsor or local regulatory agency terminates the study.

The Early Withdrawal visit will include:

- A1C (central laboratory)
- Review of concomitant medications
- Weight
- Vital signs
- Assessment of AEs
- Insulin delivery metrics (e.g., TDI, average basal and bolus insulin dose, and time on device) (Control group only)
- Completion of questionnaires (Table 2: Patient Reported Outcomes (Questionnaires))
- Return BG meter, Ketone meter, and study CGM, if unused
- Return Omnipod 5 System (Intervention group only)
- Stop CGM data collection
- Data Portal discontinuation (Intervention group only)
- Complaints/device deficiencies such as occlusion alarms and system hazard alarms since last visit
- BG/ketone meter data review by clinician
- Pump and CGM data review by clinician

The reason for withdrawal will be recorded, and their participation in the study will end.

In the event of a participant's death during the study, the participant's participation will be considered terminated, and the date of death will be used as the date of study exit.

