An event that occurs solely due to participant (i.e., user) error in which the device functions properly generally will not be considered an ADE unless it is determined that the instructions on the screen of the device or user manual (or similar training materials) may have contributed to the event (note: the event may still meet criteria for reporting as an adverse event).

Serious Adverse Device Effect (SADE): A serious adverse device effect is defined as an adverse device effect that has resulted in any of the consequences characteristic of a serious adverse event.²²

Anticipated Serious Adverse Device Effect (ASADE): anticipated serious adverse device effect (ASADE) is an effect which by its nature, incidence, severity or outcome has been identified in the risk assessment.

Device Deficiency (DD): A device deficiency is defined as a device related complaint or malfunction or any inadequacy of a device with respect to its identity, quality, durability, reliability, safety or performance and includes misuse or use errors and inadequate labeling. A device deficiency is something that happens to a device or is related to device performance, whereas an adverse event happens to a participant. A device deficiency may occur independently from an AE, or along with an AE. An AE may occur without a device deficiency or there may be an AE related to a device deficiency.

For any event where there is suspicion that the Omnipod 5 study device is involved, the Sponsor will request that the investigator return the device component for evaluation.

All device deficiencies will be reported to the Sponsor within 3 business days of knowledge of the deficiency and documented on an appropriate eCRF. Once entered, notifications will be sent automatically to Sponsor. Alternate reporting methods will be provided to site for notifying Sponsor if database entry is inaccessible. All device components associated with a reported device deficiency (Controller, Pod, and CGM) should be retained at the clinical site and returned to the Sponsor or CGM manufacturer for investigation and analysis.

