12.3.2 Evaluation of Device Deficiencies

Device deficiencies will be tabulated and listed in a manner similar to the methods described for adverse events. Any device deficiency leading to an AE or to study termination will be listed separately.

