6.6 EVALUATION OF DEVICE DEFICIENCIES

Device deficiencies will be tabulated and listed in a manner similar to the methods described for adverse events. Any device deficiency leading to an adverse event or study termination will be listed separately.

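### Section 9.10 exempts early failure and adhesion problems from the Device Deficiency Form even when an adverse event follows, so the planned listing of deficiencies leading to AEs may be incomplete

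*Protocol*

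**What the plan says.** Protocol 9.3 defines a device deficiency broadly, including shortfalls in durability, reliability and performance. It recognises that an AE may be related to a deficiency, and it states: "All device deficiencies will be reported to the Sponsor within 3 business days of knowledge of the deficiency".

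Protocol 9.10 then sets exceptions and says of them: "These occurrences are expected and will not be reported on a Device Deficiency Form". There are five items. The first two are "CGM sensor, Pod or infusion set lasting fewer days than expected per manufacturer" and "CGM tape, Pod or infusion set adherence issues". The others are Controller battery life affected by charging or heavy wireless traffic, intermittent communication faults that need no replacement, and issues (alerts and alarms included) that the user guide covers and that need no further troubleshooting.

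On output, protocol 12.3.2 says: "Any device deficiency leading to an AE or to study termination will be listed separately". SAP 6.6 says the same: "Any device deficiency leading to an adverse event or study termination will be listed separately".

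On mechanism, protocol 7.4.1 and 9.2 say that when meter glucose is at least 300 mg/dL with ketones above 1.0 mmol/L, "an occlusion or dislodged cannula should be suspected", and the Pod or infusion set is to be replaced. Protocol 9.1 names occlusion as a route to hyperglycemia or DKA.

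**The concern.** The listing in 12.3.2 and SAP 6.6 is the only planned output that connects a device failure to its consequence for the participant. It can contain only what was recorded as a deficiency. If sites are told not to record detachment or early failure, and no exception is made for cases with consequences, the listing may lack some of the cases it exists to show.

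The comparison is between a patch pump and the participant's own pump, and interruption of insulin delivery is a recognised hazard of both. A reader of the study report would expect the listing to be complete for failures that preceded ketosis or DKA, and could not tell from it that some classes of failure had been left out.

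**Working it through.** No arithmetic applies. The plan states no expected number of deficiencies or of device-caused AEs, so the check sets the sections side by side.

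1. **Are the two exemptions really unconditional?** Three of the five items in 9.10 carry a limit: battery life by its cause, communication faults by whether replacement was needed, and alerts and alarms by user-guide coverage and the absence of further troubleshooting. Short wear and adhesion carry none. Limits were written where they were wanted, so a site applying 9.10 would reasonably file no form for these two, whatever followed.

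2. **Does another section restore reporting?** Section 9.3 says all deficiencies are reported. Section 9.10 is the later and more specific text and is framed as an exception, so a site would probably follow it. If 9.3 is instead taken literally, the two sections contradict each other. Neither refers to the other.

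3. **Does the SAP settle it?** Protocol 12.7 and SAP section 1 give the SAP precedence. SAP 6.6 repeats the listing but contains no rule on which occurrences are entered as deficiencies, so the gap remains.

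4. **Can an exempt occurrence lie behind a reportable AE?** Yes, on the protocol's own description. Section 1 describes an adhesive Pod worn for up to 72 hours with the cannula directly beneath it, so loss of adhesion can plausibly dislodge the cannula. Sections 7.4.1 and 9.2 direct that the Pod or set be replaced when dislodgement or occlusion is suspected, and one replaced before its due time has had short wear. Prolonged hyperglycemia with ketones is reportable under 9.6. One episode can therefore be a reportable AE whose device cause is exempt from the form.

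5. **What is still captured?** The AE is reported (9.4, 9.6) and rated for relationship to the participant's own pump, the study CGM and Omnipod 5 (9.7). DKA and severe hypoglycemia events are adjudicated for relatedness by the Medical Monitor (10.3, SAP 6.1). AEs are tabulated by device relationship (12.3.1, SAP 6.5). Relatedness shows that a device was involved; it does not show what failed.

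6. **Does device return fill the gap?** In part. Sections 9.3 and 9.11 provide for return where Omnipod 5 is suspected of involvement. They make no such provision for a control participant's own infusion set.

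**The case against.** The strongest reply is that 9.10 screens out expected nuisance occurrences, that this is a stated design choice, and that safety capture is intact. Most of this stands. Routine short wear and peeling can stay exempt. A DKA after a detached Pod would still be reported, rated and adjudicated. The AE form or the safety management plan may also record the device cause; neither is among the documents, so this cannot be checked. The reply does not show how such a case would reach the listing that both documents promise.

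Three stronger readings are tempting, and the documents do not support them.

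- **That 9.10 bars all alarms.** It exempts an alarm only if the user guide covers it and no further troubleshooting is needed. An alarm that ends in ketone checks, a replacement and contact with the site can well be read as outside the exemption.
- **That 9.10 excludes the failure modes tied to ketosis and DKA.** Neither occlusion nor a dislodged cannula is named there. They overlap with short wear and adhesion problems but are not the same thing, so the listing may miss some such cases, not all.
- **That alarms count for participants who withdraw but not for those who complete, biasing the counts.** Section 7.9 asks at early withdrawal for "Complaints/device deficiencies such as occlusion alarms and system hazard alarms since last visit". The alarms are examples within an item that Table 1 collects at Visits 3 to 8 and at unscheduled visits too, and 9.10 does not vary by completion status. The wording also suggests that such alarms are regarded as collectable.

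**Conclusion.** The gap is real and narrow. For short wear and adhesion problems, 9.10 gives no exception when a reportable AE or study termination follows, so deficiencies of that kind have no stated route into the listing in protocol 12.3.2 and SAP 6.6. It also conflicts with 9.3 as worded. What may be lost is the link from deficiency to AE, together with some of the tabulated deficiency count. AE capture, relatedness and adjudication are unaffected, and so are the primary and secondary analyses.

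The number of AEs affected cannot be derived. It would need the frequency of early failure or detachment and the share leading to a reportable AE, and the documents give neither; a count built on assumed rates would carry no weight.

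The conclusion assumes that sites apply 9.10 literally and that no unseen form or plan already requires the link. It merits correction because a stated rule works against a stated output and the repair is small.

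**What to change.** Add one sentence to 9.10: the exceptions do not apply when the occurrence led to, or is suspected of having contributed to, a reportable AE, discontinuation of a study device or of the participant's own pump, or withdrawal from the study. In those cases the Device Deficiency Form is completed and linked to the AE where there is one. Apply the rule to both arms, so that a control participant's infusion set is treated in the same way as a Pod.

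In 9.3, make the statement that all deficiencies are reported subject to the exceptions in 9.10. If the AE form or the safety management plan already records the device cause, say so in 12.3.2 and SAP 6.6 and name it as a source for the listing.

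The cost is a few extra forms and a slightly higher reported deficiency count. No clinical management or efficacy analysis changes.

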9.11 Timing of Event Reporting

SAEs possibly related or related to a study device or study procedures and UADEs must be reported to the Sponsor/CRO within 2 business days of the site becoming aware of the event. This can occur via phone or email to the CRA/site monitor or Study Physician, or by completion of the AE eCRF. If the form is not initially completed, it should be completed as soon as possible after there is sufficient information to evaluate the event. All other reportable AEs should be submitted by completion of the AE eCRF within 5 business days of the site becoming aware of the event.

Each principal investigator is responsible for reporting adverse events required by this protocol and abiding by any other reporting requirements specific to his/her Institutional Review Board or Ethics Committee.

Upon receipt of a USADE report, the Sponsor will investigate the UADE and if indicated, report the results of the investigation to all participating investigators, overseeing IRBs or ECs, and Regulatory Authorities within 7 calendar days of the Sponsor becoming aware of the USADE. Copies of the associated reports and correspondence with the investigators, regulatory authorities, and Sponsor must be retained with study records.

The Medical Monitor will determine if the USADE presents an unreasonable risk to participants as described in the safety management plan (SMP) and in accordance with local regulations.

Device deficiencies will be handled by the Sponsor or designee.

If the participant is hospitalized because of or during the course of an SAE, then a copy of the hospital discharge summary should be requested for inclusion with the SAE documentation. In case of death, the investigator must make every effort to obtain a copy of the death certificate to submit to the Sponsor. When submitting copies of documentation, all participant identifying information must be redacted and only the unique participant number will be used to label the forms for identification purposes. All relevant documents in the local language should be summarized in English on the Case Report Form.

For any event where there is suspicion that the Omnipod 5 device is involved, the investigator will return the device for evaluation when possible.

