9.4 Reportable Adverse Events

Adverse events will be assessed on an ongoing basis throughout the study. Adverse event reporting will begin at the start time of the standard therapy (i.e., insertion of the CGM sensor) and continue until the participant's participation has ended. All adverse events must be followed until resolution, or until the AE has stabilized, or until the study has been completed.

Pre-existing medical conditions or symptoms observed prior to the start time of the standard therapy phase will not be recorded as an AE and should be collected in the participant's medical history. In the event there is a change (i.e., worsening) in the pre-existing medical condition or symptoms after enrollment meeting the criteria of a reportable adverse event, then an AE must be reported.

For this protocol, a reportable adverse event includes any untoward medical occurrence that meets one of the following criteria:

1. An SAE
2. An ADE unless excluded from reporting in Hypoglycemic Events and Hyperglycemic/Ketotic Events sections below
3. An AE not related to a study device issue which leads to temporary or permanent discontinuation of the study devices or the participant's own insulin pump, or creates a clinically significant impact on a participant's glucose control
4. An AE that affects the participant's ability to complete any study procedures
5. An AE for which a visit is made to a hospital emergency department
6. Hypoglycemic Events as defined below
7. Hyperglycemia/Ketotic Events as defined

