9.5 Hypoglycemic Events

Hypoglycemia is only reportable as an adverse event when one of the following criteria is met:

- Severe Hypoglycemia: The event required assistance of another person due to altered consciousness, and required another person to actively administer carbohydrate, glucagon, or other resuscitative actions²¹. This means that the participant was impaired cognitively to the point that he/she was unable to treat himself/herself, was unable to verbalize his/her needs, was incoherent, disoriented, and/or combative, or experienced seizure or loss of consciousness. These episodes may be associated with sufficient neuroglycopenia to induce seizure or loss of consciousness. If plasma

glucose measurements are not available during such an event, neurological recovery attributable to the restoration of plasma glucose to normal is considered sufficient evidence that the event was induced by a low plasma glucose concentration.

- Hypoglycemia resulting in an SAE that may not otherwise meet the definition of Severe Hypoglycemia defined above.

When a hypoglycemic event meets the above reporting requirements, an Adverse Event Form should be completed. A severe hypoglycemia event should be considered a serious adverse event and follow the SAE reporting requirements.

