10 STOPPING CRITERIA

10.1 Participant Discontinuation of Study Participation

In the case of a USADE for Intervention group participants, the Medical Monitor will determine if the use of the investigational device will be suspended while the problem is diagnosed. The use of the investigational device may continue if the Medical Monitor believes the event is explainable, unlikely to reoccur and that it is safe for the participant to continue using the device. Alternatively, the Medical Monitor may request the study participant, or all study participants, to stop using the investigational device or to only use in Manual Mode. Should Intervention group study participants be required to stop using the study device or to only use in Manual Mode due an USADE, use of the study device or Automated Mode will not be restarted until approval is received from the regulatory authorities.

Use of the investigational device by a participant will be discontinued if any of the following occur:

- The investigator, sponsor, or Medical Monitor believes it is unsafe for the participant to continue in the study for any reason. This could be due to the development of a new medical condition or worsening of an existing condition; or participant behavior contrary to the indications for use of the device that imposes on the participant's safety.
- The participant requests that the treatment be stopped
- Participant pregnancy
- Two distinct episodes of DKA as defined above
- Two distinct severe hypoglycemia events as defined above
- One episode of DKA and one severe hypoglycemia event as defined above

An additional requirement for continued study device use following a single DKA or severe hypoglycemia event will be that (1) the site investigator believes that the event is explainable, unlikely to recur, and that it is safe for the participant to continue to use the system and (2) the Medical Monitor concurs. If the Medical Monitor determines that the occurrence of the event indicates that it is not safe for the participant to continue to use the system, use will be discontinued, and the participant will be withdrawn from the study.

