10.3 Safety Signal Detection

Selected data from this study will be reviewed periodically to detect as early as possible any safety concern(s) related to the device so that Investigators, clinical study participants, regulatory authorities, and IRBs/IECs will be informed appropriately and as early as possible.

The Medical Monitor will conduct adjudication of any events of DKA or severe hypoglycemia or any additional events as requested by the Sponsor. The specified events will be adjudicated to determine:

- event relatedness to the study procedures and/or the devices (participant's own insulin pump, study CGM and Omnipod 5)
- whether an adverse event is unanticipated

The adjudication decision of the Medical Monitor will be used for the final classification of events, including relatedness to the study procedures and/or the devices, for the determination of safety endpoints and for all regulatory reports, product labeling, and publications or presentations.

Detailed roles and responsibilities of the Study Physician and Medical Monitor are described in the SMP.

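### The 2-business-day SAE deadline in 9.11 depends on the site's own relatedness rating, so severe hypoglycemia or DKA rated unrelated may reach the Medical Monitor 3-5 calendar days later, although 10.1 and 10.3 apply whatever the rating

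*Protocol*

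**What the plan says.** Protocol 9.11 sets two clocks, both running from the moment the site learns of the event.

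- Short clock: "SAEs possibly related or related to a study device or study procedures and UADEs must be reported to the Sponsor/CRO within 2 business days".
- Long clock: "All other reportable AEs should be submitted by completion of the AE eCRF within 5 business days of the site becoming aware of the event".

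Section 9.4 says that "a reportable adverse event includes any untoward medical occurrence that meets one of the following criteria", and the first criterion is simply that the event is an SAE. Under 9.7 the investigator rates relatedness as Unrelated, Possibly Related or Related.

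For the two events of most interest, 9.5 says: "A severe hypoglycemia event should be considered a serious adverse event and follow the SAE reporting requirements". Section 9.6 says the same of DKA.

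Three later provisions rely on the Medical Monitor:

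- **9.12:** SAE review normally takes place within 24 hours, counted from the report.
- **10.3 (and SAP 6.1):** the Medical Monitor adjudicates relatedness for every DKA or severe hypoglycemia event, and that decision is final.
- **10.1:** "An additional requirement for continued study device use following a single DKA or severe hypoglycemia event will be that (1) the site investigator believes". Under this first condition, the investigator must judge what happened to be explained and unlikely to happen again, and continuing to be safe. The second condition is the Medical Monitor's agreement.

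For comparison, 9.3 says: "All device deficiencies will be reported to the Sponsor within 3 business days of knowledge of the deficiency and documented on an appropriate eCRF".

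**The concern.** The site's initial rating selects the reporting clock, yet for severe hypoglycemia and DKA that rating is what the Medical Monitor is asked to review and may overturn. The events where the site is most confident that nothing is device-related are therefore the ones on which the independent check starts latest.

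The cross-references in 9.5 and 9.6 do not settle the matter. They send every such event to the SAE reporting requirements, but the only deadline in 9.11 that names SAEs is conditional on relatedness. Section 14.8 also only points back to the protocol's own timeline.

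At stake is the timeliness of safety oversight. No efficacy endpoint, sample size or error rate is affected. The order of priorities also looks unintended: a device deficiency that harmed nobody is due in 3 business days, sooner than a DKA or a death that the site rates Unrelated, which is due in 5.

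**Working it through.** The plan gives no figure to reproduce. The check has two parts.

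**1. Which clock applies to a severe hypoglycemia or DKA event?**

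| Site rating | SAE? (9.5, 9.6) | Deadline (9.11) | Final relatedness by Medical Monitor? (10.3) | Concurrence needed for continued device use? (10.1) |
|---|---|---|---|---|
| Related or Possibly Related | yes | 2 business days | yes | yes |
| Unrelated | yes | 5 business days | yes | yes |

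Only the deadline column changes with the rating.

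**2. How long is the difference?**

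Inputs: 2 and 5 business days (9.11) and a 24-hour review (9.12). Assumptions: a Monday-to-Friday working week, no public holidays, the day of awareness counted as day 0, and the report passed to the Medical Monitor on the day it is made. The deadline is the k-th working day after awareness; the calendar delay is that date minus the awareness date.

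| Site becomes aware on | 2 business days | 5 business days | Difference | Review by (2-day track) | Review by (5-day track) |
|---|---|---|---|---|---|
| Mon, Tue, Wed | 2 days | 7 days | 7 - 2 = 5 | 2 + 1 = 3 | 7 + 1 = 8 |
| Thu, Fri | 4 days | 7 days | 7 - 4 = 3 | 4 + 1 = 5 | 7 + 1 = 8 |
| Sat | 3 days | 6 days | 6 - 3 = 3 | 3 + 1 = 4 | 6 + 1 = 7 |
| Sun | 2 days | 5 days | 5 - 2 = 3 | 2 + 1 = 3 | 5 + 1 = 6 |

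For weekday awareness, the latest compliant report on an event rated Unrelated comes at 7 calendar days, against 2-4 for the same event rated Possibly Related. Review follows at about 8 days against 3-5. Because the 24 hours start at reporting, they add the same day to both tracks and recover none of the difference. Public holidays would lengthen both intervals.

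**The case against.** **10.1 is not suspended by 9.11.** A reader might infer that a participant may stay on the device for the whole reporting gap without the Medical Monitor's agreement. The text does not support that. Section 10.1 makes concurrence a condition of continued use, with no relatedness filter; 9.11 only fixes the latest date for a report. A site that continued use for a week without seeking concurrence would breach 10.1. This objection stands in full. What remains is that 10.1 gives no time by which concurrence must be sought, so the only stated time limit for the site's report is the one in 9.11.

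**The first event is not unknown.** A reader might also infer that a second event could occur before the first has come to light. But the clock starts at site awareness, so the investigator already knows of it. The two-event rule in 10.1 operates without a Medical Monitor decision, and the investigator may stop use on safety grounds alone. This stands too.

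**Final classification is unaffected.** The Medical Monitor's decision overrides the site's rating whenever it arrives. That holds for the safety tables, but not for the aim in 10.3 of finding safety concerns as early as possible.

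**The slow track is narrow.** Possibly Related in 9.7 has a low threshold, so few events may be rated Unrelated; the documents give no estimate. Still, 9.3 is divided on user error: a note to the ADE definition includes it, while a later paragraph says that an event due solely to user error with a properly working device is generally not an ADE. An Unrelated rating for severe hypoglycemia or DKA is therefore realistic.

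**The Safety Management Plan may already deal with this.** 10.3 places the Medical Monitor's detailed duties there, and it was not available. If it sets a shorter time, 9.11 still needs to agree with it.

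**Conclusion.** The concern holds as an inconsistency in the reporting rule. Section 9.11 allows a severe hypoglycemia or DKA event rated Unrelated to be reported 3-5 calendar days later than the same event rated Possibly Related, although 9.5, 9.6, 10.1 and 10.3 treat the two alike. The clock therefore does not support the checks that depend on it.

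The size should not be overstated. Seven calendar days is the total from weekday awareness; the part due to the rating is 3-5 days. Only SAEs rated Unrelated and not treated as unanticipated device effects are clearly affected. Events related only to a Control participant's own pump are a possible addition: the Protocol Summary lists that pump under study devices, while 9.4 names it separately from them. The Medical Monitor does not decide continued use alone, and the plan does not permit use without concurrence.

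The conclusion rests on the calendar assumptions above and on the protocol text without the Safety Management Plan. It is a modest but worthwhile correction to safety oversight.

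**What to change.** In 9.11, put all SAEs, regardless of relatedness or study group and expressly including every severe hypoglycemia and DKA event, under the existing 2-business-day deadline together with unanticipated device effects. Use one term for the latter: 9.11 has both UADE and USADE, and 9.3 and the glossary define only USADE. Keep 5 business days for non-serious reportable AEs. Then reconcile 9.11 with 9.5, 9.6, 10.1 and 10.3, and with the Safety Management Plan. The clinical criteria in 10.1 stay as they are.

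The latest compliant report on any SAE would then come 2-4 calendar days after awareness, and review at about 3-5 days. The change removes the dependence on the site's rating; it does not remove the 2-4 days, which already apply to related events.

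The cost is one amended sentence and faster reporting of a small number of unrelated SAEs. No new data or staff are needed.
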